## 2.2 Rationale for Study Design

### 2.2.1 Participant selection

Young PWID face significant challenges engaging with traditional medical care, due to a combination of factors. Mutual mistrust within the medical system works against engagement with a traditional, office-based healthcare status. Desire for confidentiality regarding drug use behaviors, especially among those using parental health insurance, may prevent engagement in care. A decreased perception of risk from HCV, which has a long latency period, may prevent young adults from prioritizing care for this disease. While perceived barriers to receiving treatment are high, and the perceived individual benefit is low, there is likely to be a significant societal benefit to treating this population due to the potential to prevent transmission among injection networks. HIV co-infected individuals are being excluded, because unlike their HIV-uninfected counterparts, significantly more monitoring and engagement than can be offered in our study will be needed for this population to address their HIV disease.

### 2.2.2 Treatment regimens used

The ability to provide same-day treatment is only feasible because of the introduction of pangenotypic antiviral regimens in which drug selection and dosing are identical for every HCV genotype and regardless of severity of liver disease. We have chosen one such regimen, sofosbuvir/velpatasvir, as our drug of choice for this study.

### 2.2.3 Schedule of follow up and monitoring

In keeping with the overall purpose of the intervention, medical visits will be limited to only those that are necessary for successful treatment. Current 12-week regimens are well-tolerated with minimal toxicity in most patients. At enrollment, HCV RNA PCR, chemistry, liver enzymes, blood count, HIV status, HBV status, and a test for liver fibrosis (imaging or laboratory), and a pregnancy test (for female patients) will be ordered. HCV RNA positive patients in the intervention arm will be asked to start medications after results of laboratory testing are reviewed. After medication start, one laboratory visit will be scheduled at 4 weeks to monitor liver enzymes and assess for on-treatment response via HCV PCR. Subsequently, liver enzymes and HCV PCR will be drawn at the end of treatment and 12 weeks of follow up to confirm response and cure. The purpose of the final monitoring visit will be to assess for HCV reinfection. Additional testing may be done if deemed necessary by clinical staff or to follow-up on abnormal results. Apart from the 4 study visits, the participants will each be contacted at least monthly by secure text message or phone call, and additional visits scheduled only if requested by the participant or deemed necessary by clinical staff. Participants randomized to the control arm, and HCV-negative participants in the intervention arm, will have text message or phone check in every month to determine their HCV treatment status., and study visits every 12 weeks for questionnaire, interview, and HCV RNA testing.

### 2.2.4 Outcome selection

The primary outcome of SVR12 is selected as a binary measure, due its use as a surrogate marker for HCV cure. Secondary outcomes will assess movements of participants along the HCV treatment continuum, and allow for identification of participants who were lost to follow up during treatment, a potentially important outcome in this population. There is concern that a participation of current PWID may be subject to reinfection after cure, and we will assess for this by repeating HCV RNA at 48 weeks. While longer follow-up for reinfection would be valuable, we do not feel it is feasible in the current study. Finally, to assess the acceptability of this intervention, examine its impact on substance use behaviors and injection risk, and to refine future iterations, we will solicit participant outcomes via survey and interview.

## 2.3 Summary of Risks and Benefits

Potential risks of the study include:

- Breach of confidentiality regarding drug use behaviors and hepatitis C disease status
- Adverse events from HCV treatment
- Adverse events from study related laboratory and imaging tests
- In the event of treatment failure, there is a risk of resistance developing to the treatment regimen
- Emotional distress from survey and interview questions pertaining to sensitive topics including mental illness, sexual health, and substance use behaviors.

Potential benefits of the study include:

- In the intervention arm, easily accessible HCV treatment that bypasses insurance authorization procedures and associated benefits of HCV cure
- Linkage to harm reduction services for PWID, with facilitated referral to substance use treatment if interested
- Public health benefit of HCV treatment in PWID, in terms of theoretical reduction in transmission potential.
- Financial compensation for participation in study procedures

### 3.0 Study Design

This is a single-center, open-label, randomized controlled trial, in which 72 HCV antibody positive participants between ages 18-29 will be recruited in two parts. During Part A, participants will be randomized to either the rapid treatment intervention arm, or the usual care control arm. During Part B, participants will be enrolled to the telemedicine arm. Recruited individuals must have used injection drugs in the past 30 days, have no medical contraindication to sofosbuvir and velpatasvir treatment, be HIV uninfected, and be HCV treatment naïve. During part B, they must have access to technology that allows telemedicine interventions (eg telephone, smartphone, or internet connection).

The goal of the study is to provide same-day, easily accessed medical evaluation and treatment to the intervention arm. During part A, participants randomized to the intervention will receive medical evaluation, laboratory assessment including confirmatory HCV RNA testing, baseline questionnaire/interview, and distribution of a 7-day medication “starter pack” on the day of enrollment. Participants who are HCV RNA negative will be notified by phone call, be asked to return their medications but continue to be followed for research visits every 12 weeks, similar to the control-arm. During part B, participants will have the option of an in-person evaluation at the syringe service program or a telemedicine visit on the day of enrollment or the following day. They will receive community based laboratory testing at a location that is convenient to them, and participate in study interview.

During part A, HCV RNA positive participants in the intervention arm will be asked to start medications, and return to pick up an additional 21-day supply. They will receive weekly text messages during treatment to record adherence. They will receive one follow-up medical visit at 4 weeks with laboratory evaluation, with distribution of the remainder of medications, and another visit at the end of treatment. One of these two visits (the participants’ choice) will include counseling for prevention of reinfection. They will then have HCV RNA PCR testing at end of treatment and 12 weeks post treatment, and at 48 weeks to assess for reinfection. Each study visit will include a brief questionnaire and qualitative interview.

Participants in the control arm will be provided facilitated referral to community HCV providers by an on-site care coordinator already facilitating care at the community site. HCV RNA negative participants will be called to inform them of these results, and then discontinued from the study. HCV RNA positive participants will be asked during the semi-structured interviews as at 12, 24, 36 and 48 week if they engaged in HCV treatment to assess whether their HCV referral has been filled, and to record their current HCV treatment status. They will also receive repeat HCV RNA testing at week 12, 24, and 48. Participants that have started treatment will be asked to sign consent for release of medical records pertaining to HCV-related laboratory testing to determine achievement of treatment response.

During part B, HCV RNA positive participants will have a 28-day supply of medications delivered, or available for pickup, as they prefer. The schedule of visits will be similar except that laboratory testing at week 4 will be optional, and all visits will be offered through telemedicine.

The three arms will be compared for the main outcome of SVR12 using a modified intention to treat analysis in which participants will be analyzed in the group they are randomized except for those who are (a) discontinued due to HCV RNA negative status or (b) found to have previously undiagnosed HIV at enrollment. Secondary outcomes will be compared using the same modified intention to treat design.

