## 6.3 Incident HIV infection

Participants who are initially HIV negative but seroconvert to HIV during the study will remain included in the study. They will be analyzed with the arm in which they were randomized. They will be offered to linkage to HIV primary care at an HIV provider local to them.

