### 8 Statistical and analytic considerations

#### 8.1 Sample size

Our own data (and others) suggests a SVR12 rate of 85% in active PWID (30), and existing literature suggests the control arm will have a very low uptake of HCV treatment (12% initiate treatment). (16) Using these estimates and an alpha =0.05, we have 100% power to detect a difference. However given the available referral and linkage programs, the control arm may have better HCV uptake and SVR 12 rates than predicted by literature. Assuming 41% (11/27) of participants in the control arm achieve SVR12, we will have 80% power to detect an SVR of 78% in the intervention arm.

In addition to have an adequate sample size to compare the primary end point of SVR12 rates with the control arm, a sample size of 27 HCV infected participants in Rapid Treatment arm allows for 90% power to show with reasonable certainty that the underlying true SVR12 rate is greater than 60% in the Rapid Treatment arm, assuming that this true rate is actually 85%.

The table below also shows two-sided exact Blyth-Still-Casella (BSC) 90% CIs for potential observed SVR proportions for 27 enrolled participants. With a HCV infected sample size of 27 participants, the CI for the true SVR12 rate will be entirely above 60% if 21 or more of the 27 participants achieve SVR12.

Patients enrolled and found not to have detectable HCV RNA will be replaced. Assuming 75% of HCV antibody positive individuals will be infected with HCV (positive HCV RNA), we anticipate have to enroll roughly 36 participants in each arm to acquire 27 with confirmed viremia.

Observed SVR12 Rate	90% CI for True SVR12 Rate
85% (23/27)	(71%, 93%)
81% (22/27)	(65%, 90%)
78% (21/27)	(62%, 90%)
74% (20/27)	(58%, 85%)
70% (19/27)	(54%, 84%)
67% (18/27)	(50%, 80%)

As of this amendment, data from part A will be analyzed based on enrollment through March 1 2020, so the power to detect a difference will be reduced from the above calculation. This is due to the break in enrollment that was necessary during the COVID-19 pandemic.

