## 8.3 Data Analysis

### 8.3.1 Analysis of clinical outcomes data

For the primary analysis, after the completion of part A, we will compare the proportion of patients who achieve SVR12 in each arm using Chi-square or Fishers’ exact testing, using an intention-to-treat approach in which participants are analyzed in the group to which they are randomized. Participants with negative confirmatory HCV RNA PCR tests on study entry will not be included in the analysis.

For secondary analyses, we will:

- Compare the proportion of patients who achieve end-of-treatment response using Chi-square or Fishers’ exact testing
- Compare the proportion of patients who complete treatment, using Chi-square or Fishers’ exact testing
- Compare the proportion of patients who have HCV reinfection, using Chi-square or Fishers’ exact testing
- Describe adherence for participants in the Intervention arm only
- Describe demographic, clinical and behavioral factors for participants who have HCV reinfection or incident HCV infection

We will also perform the same analyses using an “as-treated” approach, in which participants in the intervention arm will not be included if they failed to initiate HCV treatment, or discontinued treatment for reasons clearly unrelated to the treatment intervention (e.g. relocation, incarceration).

After the completion of part B, we will compare the proportion of patients who achieve SVR12 in each Part B telemedicine to (1)Part A intervention (2) Part A control, using Chi-square or Fishers’ exact testing, using an intention-to-treat approach in which participants are analyzed in the group to which they are randomized. Participants with negative confirmatory HCV RNA PCR tests on study entry will not be included in the analysis.

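### Sections 3.0 and 8.3.1 define different analysis sets for SVR12: 3.0 ties the RNA-negative exclusion to being discontinued and adds an HIV exception that 8.3.1 lacks

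*Combined protocol and SAP*

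**What the plan says.** **Section 3.0 (final paragraph).** The three arms are compared on SVR12 by a modified intention-to-treat analysis. It leaves out participants "a) discontinued due to HCV RNA negative status or (b) found to have previously undiagnosed HIV at enrollment", and the same set is to serve the secondary outcomes.

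**Section 8.3.1.** The primary analysis is called intention-to-treat, and its one exclusion reads: "Participants with negative confirmatory HCV RNA PCR tests on study entry will not be included in the analysis". There is no arm restriction and no HIV exception. The Part B comparison carries the same rule.

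**Follow-up of RNA-negatives.**
- Section 3.0, control arm: "HCV RNA negative participants will be called to inform them of these results, and then discontinued from the study".
- Section 3.0, Part A intervention arm: they will "be asked to return their medications but continue to be followed for research visits every 12 weeks".
- Section 1.4.1: RNA-negatives are replaced but stay under follow-up, with no distinction by arm.
- Section 5.5: every control participant, whatever the RNA status, is tested at weeks 24 and 48.

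**HIV.**
- Section 5.2.2 requires a negative antibody before consent and randomization.
- Section 2.2.3 lists HIV status among the tests ordered at enrollment.
- The Part A and Part B schedules show the antibody at screening, week 24 and week 48, with no week 0 entry.
- Section 6.3: "Participants who are initially HIV negative but seroconvert to HIV during the study will remain included in the study", analyzed in the arm to which they were randomized.

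**The concern.** The primary denominator should follow from one rule that uses baseline information only. Here two current sections give two rules. The one in 3.0 depends on discontinuation, a follow-up status that the protocol describes inconsistently. Taken with the rest of 3.0, it drops RNA-negatives from the control arm and keeps them in the intervention arm. Taken with 1.4.1 and 5.5, nobody is discontinued for being RNA-negative and the rule drops no one. SVR12 is defined relative to the end of treatment (section 1.6), and RNA-negatives are not treated, so any who are kept dilute the arm they sit in.

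The HIV exception is a further post-randomization exclusion that appears in only one of the two sections. In an open-label trial, two available denominators leave a choice that could be made after results are seen.

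**Working it through.** **Inputs (section 8.1 unless noted).** Control SVR12 41% (11/27); intervention 78% (21/27); alpha 0.05; 27 viremic and about 36 enrolled per arm; 75% of antibody-positives viremic. Allocation is 1:1 (8.2). The test is chi-square or Fisher's exact (8.3.1). Sidedness is not stated; two-sided is assumed.

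**Step 1: the plan's own figures.** The plan states "Assuming 41% (11/27) of participants in the control arm achieve SVR12" and then "we will have 80% power to detect an SVR of 78% in the intervention arm". The normal approximation is

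power = Φ{ [|p2 − p1| − 1.96·√(p̄(1−p̄)(1/n1+1/n2))] / √(p1(1−p1)/n1 + p2(1−p2)/n2) }.

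With p1 = 0.41, p2 = 0.78, n1 = n2 = 27 and p̄ = 0.595: (0.37 − 1.96 × 0.1336)/0.1238 = 0.874, so power is 80.9%. Exact enumeration at 11/27 v 21/27 gives 80.1% (uncorrected chi-square) and 72.0% (Fisher). Enrollment: 27/0.75 = 36. The stated figures reproduce, and they do so for the 8.3.1 set, viremic participants only in both arms.

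**Step 2: 3.0 taken literally.** Expected RNA-negatives per arm: 36 − 27 = 9. Controls stay at 27 and the intervention arm becomes 36. The documents do not say how an RNA-negative would be scored; here each counts as not achieving SVR12.

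- Intervention rate: 27 × 0.78/36 = 58.5% (21/36 = 58.3%).
- Difference: 58.5 − 41 = 17.5 points, against 37.
- Normal approximation, p̄ = 0.51: (0.175 − 1.96 × 0.1273)/0.1253 = −0.594, so power is 27.6%.
- Exact enumeration, 27 binomial outcomes plus 9 fixed failures:

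| True intervention rate in viremic | Test | 27 v 27 | 27 v 36 |
|---|---|---|---|
| 21/27 | chi-square | 80.1% | 27.1% |
| 21/27 | Fisher | 72.0% | 23.2% |
| 85% | chi-square | 94.4% | 45.0% |

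At the plan's example counts, Fisher's p is 0.012 for 11/27 v 21/27 and 0.21 for 11/27 v 21/36.

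**Step 3: sensitivity.** With 3, 6 or 12 RNA-negatives kept instead of 9, the normal approximation gives 60.7%, 42.0% or 17.6%. If the control rate were the 12% that 8.1 takes from the literature, power with 9 kept would still be 98.4%. If the 9 were scored as SVR12 instead, Fisher power would be 93.1%, but the type I error at 41% in both arms would be 17.6%. The direction of the error therefore depends on a scoring rule that the plan does not give.

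**Step 4: the HIV exception.** Removing one person moves the intervention rate from 21/27 = 77.8% to 20/26 = 76.9% or 21/26 = 80.8%. It moves the control rate from 11/27 = 40.7% to 10/26 = 38.5% or 11/26 = 42.3%. The shift is 0.9 to 3.0 points. Removing one or two per arm leaves power at 79.3% or 77.7%.

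**Step 5: classing a positive HIV test.** HIV undiagnosed at enrollment is excluded (3.0), and later seroconversion is kept (6.3). With the antibody already negative before randomization and no week 0 test in either schedule, the next scheduled test is at week 24. For intervention participants that is also the SVR12 visit (1.4.2). No text says which test or sample decides the class.

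**The case against.** The strongest reply is that the intent is plain. Section 8.3.1 is the analysis section and excludes entry RNA-negatives with no arm restriction. The amendment rationale for section 8 (0.2, item 9) repeats that rule for Part B as the existing approach. RNA-negatives are replaced, and the trial is sized on 27 viremic per arm. All of this stands. A reader might infer that the trial will exclude RNA-negatives from one arm only and so lose most of its power; the documents do not support that. An analyst would have to set 8.3.1 aside, follow 3.0 against 1.4.1 and 5.5, and score the extra participants as failures.

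A reader might also infer that undiagnosed HIV cannot be told apart from seroconversion. That goes too far. The text separates the two by time. Section 2.2.3 orders HIV status at enrollment, 5.2.2 allows HIV-1 RNA PCR as necessary, and Part A plasma is stored at week 0 in both arms (5.1, 5.8). Someone with a documented negative entry antibody who is positive at week 24 falls most naturally under 6.3 and stays in; mainly an infection in the window period before entry is unclear.

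Nor do the documents show that the exclusion would be decided with SVR12 known. Week 24 is the SVR12 visit only for those treated on schedule, 5.5 expects later treatment in controls, and the endpoint runs to week 48.

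What the reply does not remove is that 3.0 is current text, conflicts with 8.3.1 on label, RNA rule and HIV rule, and depends on a follow-up status described in contradictory ways.

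**Conclusion.** The concern holds as a conflict between two current definitions of the primary analysis set. Section 3.0 is the one that is wrong as written; 8.3.1, the replacement rule and the sample size agree with each other. It should be corrected, and doing so needs no change to the design.

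The fall in power from 80% to 27% is a worst case. It assumes that 9 RNA-negatives are kept in the intervention arm only, that they count as not achieving SVR12, that the test is a two-sided uncorrected chi-square, and that 27 viremic per arm are reached. The last will not apply as planned: Part A is analyzed on enrollment through March 1, 2020, section 8.1 says power is reduced, and the actual number is not given.

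The HIV part is minor. Cases should be few because a negative antibody is required before randomization, and each would shift an arm's rate by at most about 3 points at the plan's example counts. What is missing is a rule for classing a first positive at week 24.

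**What to change.** 1. Put one identical definition in 3.0 and 8.3.1: all participants randomized in Part A or enrolled in Part B, in their assigned arm, except those with a negative confirmatory HCV RNA at entry, in every arm and whether or not they are followed further. Naming Part B matters because its participants are not randomized. Use one label for the set in both places.
2. Delete the HIV exception. Alternatively, limit it to HIV shown on a named entry test or stored week 0 sample, applied identically in all arms and without reference to SVR12. Part B samples are stored only when feasible (5.8), so for that arm the rule would have to rest on a named entry test.
3. Reconcile 3.0 with 1.4.1 and 5.5 on whether control RNA-negatives are followed. Secondary outcome 4 in section 1.7 counts baseline RNA-negatives, so it needs its own stated set and cannot take the SVR12 set unchanged.

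The cost is a few sentences of wording; items 1 and 2 change no visit or treatment. The downside is that a rare participant with HIV undiagnosed at entry may stay in the denominator.

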#### 1.7 Secondary Outcomes

[figure not shown]
1. The proportion of participants who initiate treatment for HCV in the intervention arm compared to the usual care arm by study week 48.
2. The proportion of participants who complete the prescribed course of treatment for HCV in the intervention arm compared to the usual care arm by study week 48.3. The proportion of participants after initiating HCV treatment did not complete it compared to the usual care arm by study week 48.
4. The proportion of participants in both arms who achieve SVR 12, or are RNA negative at baseline, that have HCV reinfection (defined in section 5.5) by study week 48.
5. To characterize the HCV genotype and presence of resistance associated substitutions (RAS) in those treated patients with HCV reinfection or relapse.
6. To examine impact of engagement in HCV treatment on substance use behaviors and injection risk.
7. Qualitative assessment using semi-structured interviews to evaluate the acceptability of the intervention versus usual care, the barriers to initiate and complete treatment, and factors influencing successful treatment outcomes
8. To assess the feasibility, safety, and effectiveness of a tele-medicine based rapid start intervention for hepatitis C treatment in young people who inject drugs.

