## 5.5 Monitoring for reinfection

Participants in the intervention arm who receive treatment will have two post-treatment HCV RNA PCR tests, at 24 and 48 weeks, to monitor for re-infection after treatment completion. Participants who did

not receive treatment, either because of HCV-negative status or because of other reasons, will have HCV RNA PCR testing at 24 and 48 weeks. All participants in the control arm, regardless of HCV RNA status, will have HCV RNA PCR testing at 24 and 48 weeks, but it is expected that these may not be “post-treatment,” as we expect treatment initiation to be delayed for the control participants.

True reinfection will be defined as a positive HCV RNA PCR with a different HCV genotype, occurring anytime after a documented SVR 12 (negative HCV RNA PCR 12 weeks or more after treatment completion).

Participants who (1) did not have a documented SVR 12 but did have a documented end-of-treatment response or SVR 4, and subsequently have a positive HCV RNA PCR OR (2) have a positive HCV RNA PCR after documented SVR12 with the same genotype as the initial infection, will be classified as possible reinfections. These participants will then be reclassified as either true reinfections or relapses based on viral sequencing of their baseline HCV infection compared to subsequent positive HCV RNA PCRs.

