### 5.6 Monitoring for incident HCV infection

Participants who had a negative HCV RNA PCR at baseline (or whose HCV RNA PCR became negative without treatment), who subsequently have a positive HCV RNA PCR will be considered incident HCV infections, but not reinfections.

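### The plan gives reinfection conflicting denominators (Sections 1.7, 3.0, 8.3.1), and the expected ratio between arms depends on which one is used

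*Combined protocol and SAP*

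**What the plan says.** Four places bear on who is counted when reinfection is compared between arms.

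- **Section 3.0** defines the modified intention-to-treat set: participants are "analyzed in the group they are randomized except for those who are (a) discontinued due to HCV RNA negative status" or found at enrolment to have undiagnosed HIV. It then adds: "Secondary outcomes will be compared using the same modified intention to treat design". RNA-positive people who are never treated or never cured stay in.
- **Section 1.7, item 4** gives reinfection its own denominator: "The proportion of participants in both arms who achieve SVR 12, or are RNA negative at baseline, that have HCV reinfection". Never-cured RNA-positive people are out, and baseline RNA-negatives are in.
- **Sections 5.5 and 5.6** define the event. True reinfection is a positive RNA with a different genotype, "occurring anytime after a documented SVR 12". A person with only an end-of-treatment or SVR4 response who later turns positive is a possible reinfection, to be reclassified by sequencing. A baseline RNA-negative participant who turns positive is handled otherwise: such cases "will be considered incident HCV infections, but not reinfections".
- **Section 8.3.1** lists the analysis, "Compare the proportion of patients who have HCV reinfection, using Chi-square" or Fisher's exact test, without saying of whom.

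The sections also disagree on control participants who are RNA-negative at entry. Section 3.0 discontinues them, while Section 5.5 tests all control participants at weeks 24 and 48 whatever their RNA status.

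**The concern.** A person can be reinfected only after cure or, for possible reinfections, after a response on treatment. The intervention is meant to produce more cures. If never-cured people are in the denominator, the arm that cures more has more people able to have the event, and its reinfection proportion rises even when the risk after cure is the same in both arms. If baseline RNA-negatives are in the denominator, they dilute the proportion, and the dilution differs by arm if only one arm keeps them.

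Section 2.2.4 names reinfection after cure as a concern in current injectors and gives it as the reason for the week 48 RNA test. A ratio that reflects the choice of denominator could be read as evidence for or against treating this population. As the text stands, two analysts could each follow it and report ratios on opposite sides of 1.

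**Working it through.** **Inputs from the documents.** 27 RNA-positive participants per arm; SVR12 of 11/27 (41%) in control and 78% (21/27) in intervention; alpha 0.05 (all Section 8.1). 36 enrolled per arm to obtain 27 RNA-positive (Sections 1.4.1 and 8.1), hence 36 − 27 = 9 RNA-negative per arm. Allocation 1:1 (Section 8.2).

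**Assumptions.** The documents give no figure for the reinfection risk r after cure. I take r equal in both arms and show 5% to 30%. Alpha is taken as two-sided. Only SVR12 achievers are counted as able to have the event, a simplification because Section 5.5 also lets some people without SVR12 be reclassified as reinfected.

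**The plan's own figure.** With 27 per arm and 41% v 78%, the normal approximation gives 80.9% power and exact enumeration of the uncorrected Chi-square gives 80.2%, so the stated 80% reproduces. (Fisher's exact test gives 72.1%.) The SVR12 inputs are therefore the ones the plan uses.

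**Expected reinfection proportion** = (number cured × r) / denominator:

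| Denominator | Intervention | Control | Ratio | At r = 10% |
|---|---|---|---|---|
| 3.0: all RNA-positive randomised | 21r/27 = 0.778r | 11r/27 = 0.407r | 21/11 = 1.91 | 7.8% v 4.1% |
| 1.7 item 4, RNA-negatives kept in both arms | 21r/(21+9) = 0.70r | 11r/(11+9) = 0.55r | 1.27 | 7.0% v 5.5% |
| 1.7 item 4, control RNA-negatives discontinued as in 3.0 | 21r/30 = 0.70r | 11r/11 = 1.00r | 0.70 | 7.0% v 10.0% |
| SVR12 achievers only | 21r/21 = r | 11r/11 = r | 1.00 | 10% v 10% |

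Under these assumptions the ratios do not depend on r.

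**Size on the 3.0 set.** The difference is (21 − 11)r/27 = 0.370r: 1.9 points at r = 5%, 3.7 at 10%, 7.4 at 20% and 11.1 at 30%. Expected events are 2.1 v 1.1 at r = 10% and 6.3 v 3.3 at r = 30%.

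**Chance of a significant result on the 3.0 set.** Fisher's test rejects in 0.6% of trials at r = 10% and 9.3% at r = 30%. The uncorrected Chi-square rejects in 5.9% and about 20%. Expected events per arm are below 5 even at r = 30% ((6.3 + 3.3)/2 = 4.8), so Fisher's test would be the usual choice.

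**Break-even.** On the 3.0 set the arms come out equal when the intervention arm's risk after cure is 11/21 = 0.52 of the control arm's. Below that, control shows the higher proportion.

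**The case against.** The strongest objection is that an outcome's own definition normally governs over a general sentence. Section 1.7 item 4 defines the reinfection denominator and leaves never-cured people out. A reader might infer from 3.0 and 8.3.1 that the plan has settled on the modified intention-to-treat set, so that the better arm must show more reinfection. The documents do not support that. They contradict themselves, and the 1.91 is an expectation under equal risk after cure. There are reasons to doubt equality: only the intervention arm receives reinfection counselling (Section 5.7), and control treatment is expected to be delayed (Section 5.5), which shortens time at risk by week 48.

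This objection stands against the stronger reading. It does not rescue the plan, because item 4 has faults of its own. It includes people who cannot be reinfections under 5.6, and it leaves out people without documented SVR12 whom 5.5 allows to be reclassified as reinfected. Even limited to SVR12 achievers, a between-arm test conditions on an outcome the intervention aims to change, so it is not a randomised comparison.

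A reader might also divide 85% by 12% from Section 8.1 and claim a sevenfold artefact. That does not hold, because the 12% is treatment initiation and not SVR12.

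It can fairly be said that a proportion on the modified intention-to-treat set is a valid randomised estimate of the effect of assignment on reinfection. It is, but it answers a different question from risk after cure, and the plan does not say which it wants.

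Finally, the numbers are small: about one event at 10% risk. Part A is cut off at enrolment through March 1, 2020, and Section 0.2 drops reinfection analysis for the telemedicine cohort. This limits the weight of the point but does not remove it.

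**Conclusion.** The concern holds as a contradiction between sections. The plan does not fix who is at risk of reinfection, and at its own SVR12 figures with equal risk after cure, the expected ratio is 1.91, 1.27, 0.70 or 1.00 depending on the section followed. It does not hold as a claim that the plan has chosen the modified intention-to-treat set, or that excess reinfection in the intervention arm is certain.

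The practical effect is a distorted estimate on very few events, not a likely false-positive test. The ratios rest on 21/27 v 11/27, nine RNA-negatives per arm, equal risk after cure, and events only in SVR12 achievers. The event counts rest also on the assumed r, and actual Part A numbers will be smaller.

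**What to change.** 1. **One denominator.** In 1.7 item 4, 3.0 and 8.3.1, define the reinfection set as participants with documented SVR12 and at least one HCV RNA result after it. Remove baseline RNA-negatives from item 4.
2. **Section 3.0.** Exempt reinfection from the sentence on secondary outcomes. Leave the other secondary outcomes on the modified intention-to-treat set.
3. **Separate reporting.** Report possible reinfections without documented SVR12 on their own line, with their classification after sequencing. Report incident infection in baseline RNA-negatives separately under 5.6, and reconcile 3.0 with 5.5 on whether control RNA-negatives are followed.
4. **Section 8.3.1.** Replace the between-arm reinfection test with a within-arm description: count, proportion with exact confidence interval, and person-time after SVR12. SVR12 is a post-randomisation outcome and control cures come later, so a p-value between arms would not have a randomised interpretation.
5. **Optional.** If a randomised comparison is wanted, compare SVR12 with no later positive RNA through week 48 on the modified intention-to-treat set. It needs a rule for missing RNA and a caveat about unequal time at risk. For example, a control participant who starts an assumed 12-week course at week 24 reaches SVR12 at 24 + 12 + 12 = week 48 and counts as a success with no time at risk. It also counts relapse together with reinfection.

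The cost is wording in three sections and a small table. Reinfection no longer carries a between-arm p-value, which the expected event counts could not have made informative.
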